**IND # 124879**

**Protocol/Study No. DSXS1538a/71515011**

**Desoximetasone 0.25% Shampoo**

---

**IND # 124879**

**Protocol/Study No. DSXS1538a/71515011**

**Desoximetasone 0.25% Shampoo**

---

## **1. INTRODUCTION**

This Statistical Analysis Plan (SAP) is based on the final Clinical Study Protocol DSXS1538a (Study No. 71515011) Rev. 2 dated December 20, 2016. The SAP provides details on the planned statistical methodology for the analysis of the study data. The SAP also outlines the statistical programming specifications for the tables, listings and figures.

This SAP describes the study endpoints, derived variables, anticipated data transformations and manipulations, and other details of the analyses not provided in the study protocol. This SAP therefore outlines in detail all other aspects pertaining to the planned analyses and presentations for this study.

The following documents were reviewed in preparation of this SAP:

- Clinical Study Protocol DSXS1538a (Study No. 71515011) Rev. 2 dated December 20, 2016
- Case Report Form Booklet Version 1.0 for Study No. 71515011 (DSXS1538a)

The reader of this SAP is encouraged to also read the clinical protocol for details on the conduct of this study, and the operational aspects of clinical assessments and timing for completing a patient in this study.

## **2. OBJECTIVES**

The objectives of this study are to:

1. Evaluate the potential of desoximetasone 0.25% shampoo to suppress HPA axis function in patients with moderate to severe scalp psoriasis.
2. Evaluate the efficacy parameters and adverse event (AE) profiles of desoximetasone 0.25% shampoo administered to patients with moderate to severe scalp psoriasis.

## **3. OVERALL STUDY DESIGN**

This open-label, safety study is designed to evaluate the potential for adrenal suppression after maximal use treatment with desoximetasone 0.25% shampoo (Taro Pharmaceuticals, U.S.A.), for the treatment of moderate to severe scalp psoriasis.

Up to 40 eligible patients with stable plaque psoriasis of the scalp that satisfy all eligibility criteria will be enrolled into the study at Visit 1 to obtain 20 evaluable patients. Patients must be overall in good health. They should have a current diagnosis of moderate to severe scalp psoriasis with IGA score of at least 3 or 4.

**NOVUM PHARMACEUTICAL RESEARCH SERVICES  
STATISTICAL ANALYSIS PLAN**

**IND # 124879**

**Protocol/Study No. DSXS1538a/71515011**

**Desoximetasone 0.25% Shampoo**

---

Up to 40 patients will be enrolled to obtain 20 evaluable patients with a confirmed diagnosis of moderate to severe scalp psoriasis.

Patients enrolled in the study will apply product once daily for 28 days, according to provided instructions. Each patient is expected to receive 28 doses of study product.

Patients will attend a total of 3 Clinic Visits and a telephone follow-up phone call (Visit 4) as follows:

- **Visit 1 (Day 1):** Screening/Enrollment
- **Visit 2 (Day 14±2):** Interim Visit
- **Visit 3 (Day 29 ± 2):** End of Study or Early Termination
- **Visit 4 (Day 42± 4):** Follow-Up Telephone Phone Call

The primary endpoint is the proportion of patients in the study with HPA axis suppression following treatment with the study medication.

The safety profile of each treatment group will be evaluated by comparing adverse events.

**NOVUM PHARMACEUTICAL RESEARCH SERVICES  
STATISTICAL ANALYSIS PLAN**

**IND # 124879**

**Protocol/Study No. DSXS1538a/71515011**

**Desoximetasone 0.25% Shampoo**

---

**Study Schematic**

|                                                     | Visit 1                                  | Visit 2   | Visit 3                                              | Visit 4                  |
|-----------------------------------------------------|-------------------------------------------------|------------------|-------------------------------------------------------------|---------------------------------|
| Day                                          | 1                                        | 14 ± 2    | 29 ± 2                                               | 42 ± 4                   |
| Procedures                                   | Screening/
Enrollment
Before 12 pm | Interim
Visit | End of
Study/Early
Termination
Before 12 pm | Telephone
Follow-Up
Visit |
| Informed Consent                                    | X                                               |                  |                                                             |                                 |
| Medical History and
Demographics                 | X                                               |                  |                                                             |                                 |
| Vital Signs                                         | X                                               | X                | X                                                           |                                 |
| Pregnancy Test*                                     | X                                               | X                | X                                                           |                                 |
| Physical Exam                                       | X                                               |                  | X                                                           |                                 |
| HEENT Exam                                          | X                                               | X                | X                                                           |                                 |
| % Scalp Affected                                    | X                                               | X                | X                                                           |                                 |
| Investigator Global Assessment                      | X                                               | X                | X                                                           |                                 |
| Concomitant Medication                              | X                                               | X                | X                                                           | X                               |
| Laboratory Evaluations                              | X                                               |                  | X                                                           |                                 |
| Cortisol Response Test                              | X                                               |                  | X                                                           |                                 |
| Confirm Inc/Exc Criteria                            | X                                               |                  |                                                             |                                 |
| Dispense Wristband                                  | X                                               |                  |                                                             |                                 |
| Weigh and Dispense Study Product                    | X                                               | X                |                                                             |                                 |
| Collect and Weigh Study Product                     |                                                 | X                | X                                                           |                                 |
| Dispense/Review Patient Diary                       | X                                               | X                | X                                                           |                                 |
| Ocular Assessment                                   |                                                 | X                | X                                                           |                                 |
| Adverse Events                                      |                                                 | X                | X                                                           | X                               |
| Evaluation of Patient Compliance
to the Protocol |                                                 | X                | X                                                           |                                 |

\* Pregnancy test will be carried out for females of childbearing potential.

**NOVUM PHARMACEUTICAL RESEARCH SERVICES  
STATISTICAL ANALYSIS PLAN**

**IND # 124879**

**Protocol/Study No. DSXS1538a/71515011**

**Desoximetasone 0.25% Shampoo**

---

#### **4. SAMPLE SIZE**

The sample size of 20 evaluable patients was deemed appropriate to meet the objective of the study.

#### **5. STUDY ENDPOINTS AND ANALYSIS POPULATIONS**

##### **Primary Outcome Measures:**

Hypothalamic Pituitary Adrenal (HPA) Axis Response to Cosyntropin demonstrating the absence or presence of adrenal suppression at the end of treatment defined by the following criteria: 30 minute post Cortrosyn™ injection level cortisol level of  $\leq 18$  mcg/100ml during the Cortisol Response Test.

##### **Safety Population:**

Safety Population includes all patients who applied at least one dose of study drug.

#### **6. STATISTICAL ANALYSIS METHODS**

If not otherwise specified, statistical significance is defined as  $p < 0.05$  and is two-tailed. Data will be summarized with respect to demographic and baseline characteristics, efficacy variables and safety variables.

For categorical variables, the number and percent of each category within a parameter will be calculated for non-missing data. For continuous variables, statistics will include number of observations, mean, standard deviation, median, minimum and maximum values.

All statistical analyses will be conducted using SAS®, Version 9.4 or higher. Datasets will be prepared using headings from Clinical Data Interchange Consortium (CDISC) Study Data Tabulation Model (SDTM) implementation for human clinical trials and ADaM (Analysis Dataset Model).

##### **6.1 Baseline Characteristics**

###### **6.1.1 Demographics**

Demographic information collected at baseline includes the following:

- Age (years)
- Gender (Male/Female)
- Ethnicity (Hispanic/non Hispanic)

**NOVUM PHARMACEUTICAL RESEARCH SERVICES  
STATISTICAL ANALYSIS PLAN**

**IND # 124879**

**Protocol/Study No. DSXS1538a/71515011**

**Desoximetasone 0.25% Shampoo**

---

- Race (White, Black/African American, Native Hawaiian or Other Pacific Islander, Asian, American Indian or Alaska Native, Other)

Summary tables will be presented. Continuous variables will be summarized using descriptive statistics (n, median, minimum, maximum, mean, standard deviation). Categorical variables will be summarized using frequencies and percentages.

All data will be listed by patient.

### **6.1.2 Medical History**

At Visit 1, patients will be questioned about medical history, including acute and chronic medical history and medical history relevant to their scalp psoriasis.

Medical history data will be listed by patient.

### **6.1.3 Physical Exam**

A general physical exam will be conducted at Visit 1 and Visit 3. The physical exam must include a dermatological examination as a minimum.

Abnormal physical exam results will be listed by patient and visit.

### **6.1.4 Percent Scalp Affected**

Patient's scalp will be examined by Investigator/designated clinician to determine the percent surface area affected with plaque psoriasis at all visits.

Descriptive summary (n, mean, standard deviation, median, minimum, maximum) will be presented for percent scalp affected by visit.

Percent scalp affected will be listed by patient and visit.

### **6.1.5 Pregnancy Test**

Urine pregnancy tests on females of child-bearing potential will be performed at Visit 1, 2 and 3.

Positive pregnancy test results will be listed by patient and visit.

### **6.1.6 Concomitant Medications**

At Visits 1-3 and during the telephone follow-up phone call (Visit 4) patients will be questioned about current and concomitant medication use over the previous 12 weeks. At all Interim Visits patients will be questioned about ongoing or new concomitant medication use.

**NOVUM PHARMACEUTICAL RESEARCH SERVICES  
STATISTICAL ANALYSIS PLAN**

**IND # 124879**

**Protocol/Study No. DSXS1538a/71515011**

**Desoximetasone 0.25% Shampoo**

---

All prior and concomitant medications taken since screening will be listed by patient.

## **6.2 Statistical Analyses**

### **6.2.1 Safety Analysis of Potential HPA Axis Suppression**

Dosing will be once daily for 28 days. Patients who have normal adrenal function at baseline, use at least 21 doses of the study product and have data from a post-treatment cortisol response test will be included in the analysis.

The primary analysis of interest is to assess the proportion of patients considered to have demonstrated possible HPA axis suppression following treatment with the study medication.

A logistic regression of the proportion of patients in the study with HPA axis suppression may be performed as exploratory analysis with % scalp affected as a covariate. This will depend on the distribution of the % scalp data collected. See Appendix D for results from the cortisol response test considered indicative of potential HPA axis suppression.

### **6.2.2 Investigator Global Assessment**

Patient will be examined to determine the severity of scalp psoriasis based on a global assessment of plaque elevation, scaling and erythema by the Investigator/designated clinician.

Investigator Global Assessment data will be summarized using frequency and percentage by visit.

Investigator Global Assessment data will also be listed by patient and visit.

## **6.3 Safety Analysis**

Safety analysis will be conducted on all patients who applied at least one dose of study drug.

### **6.3.1 Adverse Events**

All the adverse events (AEs) reported throughout the study will be coded and classified according to the MedDRA (Medical Dictionary for Regulatory Activities) coding dictionary. Each adverse event is to be evaluated for date of start and end, seriousness, severity, causal relationship with the study drugs, action taken and outcome.

All AEs will be listed by patient.

A summary table of the number and percent of patients with AEs by system organ class, preferred term will be presented. Each patient will be counted only once within each preferred term.

**NOVUM PHARMACEUTICAL RESEARCH SERVICES  
STATISTICAL ANALYSIS PLAN**

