7.4 Risks and Benefits

Known adverse reactions to topical corticosteroids include burning, itching, irritation, dryness, folliculitis, hypertrichosis, acneiform eruptions, hypopigmentation, perioral dermatitis, allergic contact dermatitis, maceration of the skin, secondary infection, skin atrophy, striae and milia. Dosing for extended periods of time may result in suppression of adrenal function.

Cortrosyn™ for injection is intended diagnostic and not therapeutic use and adverse reactions other than a rare hypersensitivity reaction are not anticipated. Known reactions are slight whealing with erythema at the site of injection.

The subject may benefit from clearing of the lesions and improvement of the condition of the disease. If the drug is approved, then many patients may benefit from its use.

CONFIDENTIAL PROTOCOL

An Open Label, Safety Study to Assess the Potential for Adrenal Suppression Following Maximal Use Treatment with Desoximetasone 0.25% shampoo(Taro Pharmaceuticals U.S.A., Inc.) in Patients with Scalp Psoriasis

The potential risks and benefits of participation in the study will be explained to the patient verbally and written in the informed consent form.

All patients enrolled in this study will receive the benefit of free specialized medical care, beyond standard medical treatment that would be expected through most health insurance plans. In addition, the patient will receive a stipend as compensation for time and inconvenience related to study participation including costs associated with travel to and from the medical facility.

Ethical consideration related to this protocol and the use of human patients will be reviewed by an IRB.

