9.5.2 Visit 2 (Day 14 ± 2): Interim Visit

1. **Pregnancy Test:** A pregnancy test will be required of all females of child bearing potential prior to enrollment.
2. **Vital Signs:** The patient's vital signs will be recorded (pulse, blood pressure, temperature and respiration rate).
3. **HEENT Examination:** A general exam of the head, eyes, ears, nose and throat will be conducted at the clinic.
4. **% Scalp Affected:** Patient's scalp will be examined by Investigator/designated clinician to determine the percent surface area affected with plaque psoriasis. Refer to Appendix B
5. **Investigator's Global Assessment:** Patient's scalp will be examined to determine a psoriasis severity score based on a global assessment of plaque elevation, scaling and erythema by the Investigator/designated clinician (refer to Appendix A).
6. **Concomitant Medication:** Review with the patient use of new or change in ongoing concomitant medication since Visit 2.

CONFIDENTIAL PROTOCOL

An Open Label, Safety Study to Assess the Potential for Adrenal Suppression Following Maximal Use Treatment with Desoximetasone 0.25% shampoo(Taro Pharmaceuticals U.S.A., Inc.) in Patients with Scalp Psoriasis

7. **Adverse Events:** Patients will be questioned about any health status changes/adverse events since last visit. All events will be recorded.
8. **Ocular Assessments:** Patients will be questioned about any ocular discomfort as a part of safety assessments (refer to Appendix C)
9. **Evaluation of Patient Compliance to the Protocol:** Collect and review patient's dosing diary for compliance and provide a new diary. Non-compliance with dosing does not warrant dismissal from the study. Counsel non-compliant patients on dosing requirements of the study.
10. **Collect Study Product:** The used bottle of study drug will be collected and the weight recorded.
11. **Dispense Study Product:** If patient continues in the study, record weight of one bottle of study product and dispense.
12. **Provide Dosing Diary:** If patient continues in the study, provide a new dosing diary.
13. Schedule Visit 3

9.5.3 Visit 3 (Day 29 ± 2): End of Study or Early Termination, Before 12 pm

1. **Vital Signs:** The patient's vital signs will be recorded (pulse, blood pressure, temperature and respiration rate).
2. **Pregnancy Test:** A pregnancy test will be required of all females of child bearing potential.
3. **Physical Exam:** A general physical exam will be conducted.

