4. **HEENT Examination:** A general exam of the head, eyes, ears, nose and throat will be conducted at the clinic
5. **% Scalp Affected:** Patient's scalp will be examined by Investigator/designated clinician to determine the percent surface area affected with plaque psoriasis. Refer to Appendix B
6. **Investigator's Global Assessment:** Patient's scalp will be examined to determine a psoriasis severity score based on a global assessment of plaque elevation, scaling and erythema by the Investigator/designated clinician (refer to Appendix A). Patients with a score of 3 or more, indicating moderate to severe psoriasis will be included in the study
7. **Concomitant Medication:** Review with the patient use of new or change in ongoing concomitant medication since Visit 2.
8. **Adverse Events:** Patients will be questioned about any health status changes/adverse events since last visit. All events will be recorded.
9. **Ocular Assessments:** Patients will be questioned about any ocular discomfort as a part of safety assessments (refer to Appendix C)
10. **Evaluation of Patient Compliance to the Protocol:** Collect and review patient's dosing diary for compliance.
11. **Collect Study Product:** The used bottle of study product will be collected and the weight recorded.

CONFIDENTIAL PROTOCOL

An Open Label, Safety Study to Assess the Potential for Adrenal Suppression Following Maximal Use Treatment with Desoximetasone 0.25% shampoo(Taro Pharmaceuticals U.S.A., Inc.) in Patients with Scalp Psoriasis

12. **Laboratory Evaluations:** A blood sample will be collected for hematology and clinical chemistry testing. (See Appendix F).
13. **Cortisol Response Test:** All patients will have a cortisol response test performed according to the procedure detailed in Appendix D.

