9.7.3 Relationship of Adverse Event

Relationship to the Study Product

- **NOT RELATED:** Any AE that is clearly not related to use of the study drug.
- **POSSIBLE:** The association of the AE with the study drug is unknown; however, a relationship between the drug and event cannot be ruled out.
- **PROBABLE:** There is reasonable temporal relationship between the use of the study drug and the AE. Based upon the Investigator's clinical experience, the association of the event with the study drug seems likely.
- **DEFINITE:** The AE occurs following the application of the study drug and it cannot be reasonably explained by any other known characteristics of the patient's clinical state, environmental or toxic factors, or other modes of treatment administered to the patient. It disappears or decreases upon discontinuation of the study medication and reappears on a re-challenge of the study drug.

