Pregnancy Category C. Animal reproduction studies have not been conducted with CORTROSYNTM (cosyntropin) for Injection. It is also not known whether CORTROSYNTM can cause fetal harm when administered to a pregnant woman or can affect reproduction capacity. CORTROSYNTM should be given to a pregnant woman only if clearly needed.

Nursing Mothers

It is not known whether this drug is excreted in human milk. Because many drugs are excreted in human milk, caution should be exercised when CORTROSYNTM (cosyntropin) for Injection is administered to a nursing woman.

Pediatric Use

(See DOSAGE AND ADMINISTRATION section.)

ADVERSE REACTIONS

Since CORTROSYNTM (cosyntropin) for Injection is intended for diagnostic and not therapeutic use, adverse reactions other than a rare hypersensitivity reaction are not anticipated. A rare hypersensitivity reaction usually associated with a pre-existing allergic disease and/or a previous reaction to natural ACTH is possible. Symptoms may include slight whealing with splotchy erythema at the injection site. There have been rare reports of anaphylactic reaction. The following adverse reactions have been reported in patients after the administration of CORTROSYNTM and the association has been neither confirmed nor refuted:

- bradycardia
- tachycardia
- hypertension
- peripheral edema
- rash

DOSAGE AND ADMINISTRATION

CORTROSYNTM (cosyntropin) for Injection may be administered intramuscularly or as a direct intravenous injection when used as a rapid screening test of adrenal function. It may also be given as an intravenous infusion over a 4 to 8 hour period to provide a greater stimulus to the adrenal glands. Doses of CORTROSYNTM 0.25 to 0.75 mg have been used in clinical studies and a maximal response noted with the smallest dose.

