**IND # 124879**

**Protocol/Study No. DSXS1538a/71515011**

**Desoximetasone 0.25% Shampoo**

---

A frequency summary table of the number of AEs by system organ class, preferred term, severity will be presented. Severity will be classified as “Mild”, “Moderate”, or “Severe”.

Similarly, a frequency summary table of the number of AEs by system organ class, preferred term, and relationship to a study drug will be presented. Relationship to a study drug will be classified as “Not Related” or “Related” where “Related includes “Possible”, “Probable”, or “Definite”.

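### The AE tables have no treatment-emergent cut-off and no causality field for Cortrosyn, so reactions to the diagnostic injection would be counted in the shampoo's AE profile

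*SAP*

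**What the plan says.** **Scope of the AE tables.** SAP 6.3.1 says "All the adverse events (AEs) reported throughout the study will be coded and classified". SAP sections 5 and 6.3 set the population as everyone who used at least one dose, and Tables T16.1.9.7 to T16.1.9.11 carry that population in their titles. Neither the text nor the shells define a treatment-emergent event or an onset cut-off.

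**Causality.** The only scale, in protocol 9.7.3, is headed "Relationship to the Study Product". SAP 6.3.1 adds a table by system organ class, "preferred term, and relationship to a study drug will be presented", in which Possible, Probable and Definite are merged into Related. The same section once speaks of study drugs in the plural, without defining the term.

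**Injections.** In protocol 9.5.1 the cortisol test is item 12 and dispensing is item 13. The test recurs as item 13 of 9.5.3: "All patients will have a cortisol response test performed according to the procedure detailed in Appendix D". Suppressed patients are retested 28, 56 and 84 days after stopping (9.6.18).

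**AE questions.** The schematic marks adverse events at Visits 2, 3 and 4, not at Visit 1. At Visits 2 and 3, "Patients will be questioned about any health status changes/adverse events since last visit. All events will be recorded". Visit 4 is a call about new events. Section 9.6.14 makes adverse events a diary item, and 9.7 provides for monitoring throughout by solicited and unsolicited means.

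**Known reactions.** Section 7.4, beyond rare hypersensitivity, says: "Known reactions are slight whealing with erythema at the site of injection". Appendix G, the Cortrosyn label, adds "There have been rare reports of anaphylactic reaction" and names bradycardia, tachycardia, hypertension, peripheral edema and rash as reported, with the causal link neither established nor excluded.

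**The concern.** Objective 2 includes the AE profile of the shampoo. Every patient also receives a second agent with reactions of its own, the first time before any shampoo has been used. The study has one arm, so no control group shows how much of the AE profile comes from Cortrosyn. If the tables neither separate events by onset nor allow attribution to the injection, a Day 1 rash from Cortrosyn is reported in the same rows as a rash from the shampoo.

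Two related points are at stake. A reaction in a patient who never goes on to dose is counted in none of these tables, because that patient is outside the Safety Population. And if no one is asked after the injection, a mild reaction may be recorded late or not at all.

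**Working it through.** The plan states no figure to reproduce, so the check sets the provisions side by side and works out the size of one case.

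**1. Is a pre-application reaction counted?** The injection precedes dispensing at Visit 1. SAP 6.3.1 takes all reported AEs, and the population needs one dose at any time. A reaction between the injection and the first application therefore enters T16.1.9.7 to T16.1.9.10 (and T16.1.9.11 if serious) once the patient doses.

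**2. Size of one case.** Share = 1/N. The inputs are 20 evaluable and up to 40 enrolled (protocol 9.1).

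- N = 20: 1/20 = 5.0%
- N = 30: 1/30 = 3.3%
- N = 40: 1/40 = 2.5%

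Each exceeds the 2% threshold of T16.1.9.8.2, so one patient is enough at any planned size. The Safety Population may approach 40, so 2.5% is the fairer figure and 5% the extreme.

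**3. Exposure.** Two injections per completing patient: 2 × 40 = 80. A suppressed patient followed to day 84 has Visit 1, Visit 3 and three follow-up tests = 5.

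**4. Chance of at least one Visit 1 reaction.** The documents give no rate, so p per injection is an assumption: 1 − (1 − p)^N.

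| Assumed p | N = 20 | N = 40 |
|---|---|---|
| 0.5% | 9.5% | 18.2% |
| 1% | 18.2% | 33.1% |
| 2% | 33.2% | 55.4% |
| 5% | 64.2% | 87.1% |

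The range shows only that the answer depends on an unknown rate.

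**5. Attribution.** Section 9.7.3 reserves Not Related for events clearly unrelated to study drug and uses Possible when a link cannot be excluded. Section 7.4 lists irritation and allergic contact dermatitis for topical corticosteroids; Appendix G lists rash for Cortrosyn. A skin event after dosing, or on Day 1 in unknown order, could plausibly be rated Possible and so appear as Related in T16.1.9.10. No field records Cortrosyn as the cause.

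**6. What covers each injection?**

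| Injection | Cover in the documents | Interval to next AE contact |
|---|---|---|
| Visit 1, Day 1 | Diary, general monitoring, Visit 2 question | Day 14 − 1 = 13 days (11 to 15 with the window) |
| Visit 3, Day 29 ± 2 | General monitoring, Visit 4 call; the diary is collected and no new one is issued | Day 42 − 29 = 13 days (38 − 31 = 7 to 46 − 27 = 19) |
| Follow-up tests | General monitoring only | None: the first falls on Day 27 + 28 = 55 or later, after the latest call on Day 46 |

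L16.2.6.2, the follow-up listing, has no AE field.

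**7. Can Day 1 events be ordered afterwards?** L16.2.7 gives AE start date and L16.2.5.1 the date of first dose, so different-day events can be ordered. For same-day events, injection time is in L16.2.6.1 and dosing time in the diary (9.6.14). AE onset time is the missing piece in the shells.

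**The case against.** A reader might infer that Cortrosyn reactions are never asked about. The documents do not support that. The Visit 2 question covers everything "since last visit" in substance: "Patients will be questioned about any health status changes/adverse events since last visit". The diary handed out at Visit 1 takes adverse events, the Visit 4 call follows the second injection, and section 9.7 requires monitoring throughout. Patients are also on site until the 30-minute draw, when staff could see an acute reaction.

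A reader might also infer from the item numbers in 9.5.3 that the Visit 3 question is put before the injection. The order is not stated to be binding, and the schematic places the cortisol test above adverse events. What stands is narrower: nothing requires an AE question after an injection on the day.

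A third tempting reading is that a pre-application reaction would be reported as related to the shampoo. An event clearly before first use can be rated Not Related, and T16.1.9.10 shows that category separately. The risk of a Related rating is confined to unclear events after dosing or on the same day in unknown order.

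Further points deserve weight. SAP section 7 says the shells may not show every aspect of the study, and the case report form is not among the documents, so onset time may already be collected. Appendix G does not anticipate reactions beyond rare hypersensitivity, and exclusion 8 removes patients with a previous reaction. The AE tables are descriptive, and every event is also listed by patient. These points limit the consequence, but they supply neither an onset rule nor a causality field.

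**Conclusion.** The point holds in three parts: there is no onset cut-off for the AE tables, no causality field that names Cortrosyn, and no AE question required after an injection on the day. The first rests directly on the text. The second holds provided the undefined plural in SAP 6.3.1 does not include Cortrosyn; nothing in the documents says that it does. The third leaves the follow-up tests least covered.

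The size is one patient in N, 2.5% at 40, for each case that occurs. How many would occur is unknown. The primary HPA endpoint does not depend on any of this, so the impact is minor, though the changes are cheap and bear on an objective of the study.

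**What to change.** 1. **SAP 6.3.1 and T16.1.9.7 to T16.1.9.11.** Tabulate only AEs that start or worsen after the first shampoo application. List events before that point separately, including those in patients who never dose. State how a same-day event without an onset time is classed. This is SAP wording only.
2. **Protocol and case report form.** Ask the AE question at the existing 30-minute draw at Visit 1, Visit 3 and each follow-up test. Record AE onset time on Day 1, so that it can be ordered against the injection time and the diary dosing time.
3. **Protocol 9.7.3 and L16.2.7.** Add relationship to Cortrosyn beside relationship to study product. The onset rule in (1) cannot separate reactions at Visit 3 or at follow-up tests, all of which come after first application.
4. **Section 7.4 and Appendix G.** Reconcile the two accounts of known Cortrosyn reactions, keeping the label's statement that the link with bradycardia, tachycardia, hypertension, peripheral edema and rash is unresolved.

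No extra visit is needed, because the patient is already present for the 30-minute sample. The cost is slightly more data entry and, for the protocol changes, an amendment with IRB approval under section 11.2.3.
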